# 11.2.4 PROCEDURES FOR ELICITING, RECORDING, AND REPORTING ADVERSE EVENTS

# **Eliciting Adverse Events**

A cons	istent methodology for eliciting AEs at all subject evaluation time points should be adopted
Examp	les of non-directive questions include:
	"How have you felt since your last clinical visit?"
	"Have you had any new or changed health problems since you were last here?"

# **Specific Instructions for Recording Adverse Events**

Investigators should use correct medical terminology/concepts when reporting AEs or SAEs. Avoid colloquialisms and abbreviations.

# a. Diagnosis vs. Signs and Symptoms

If known at the time of reporting, a diagnosis should be reported rather than individual signs and symptoms (e.g., record only liver failure or hepatitis rather than jaundice, asterixis, and elevated transaminases). However, if a constellation of signs and/or symptoms cannot be medically characterized as a single diagnosis or syndrome at the time of reporting, it is acceptable to report the information that is currently available. If a diagnosis is subsequently established, it should be reported as follow-up information.

#### b. Deaths

All deaths that occur during the protocol-specified AE reporting period (see Section I), regardless of attribution, will be reported to the appropriate parties. When recording a death, the event or condition that caused or contributed to the fatal outcome should be reported as the single medical concept. If the cause of death is unknown and cannot be ascertained at the time of reporting, report "Unexplained Death".

# c. Preexisting Medical Conditions

A preexisting medical condition is one that is present at the start of the study. Such conditions should be reported as medical and surgical history. A preexisting medical condition should be re-assessed throughout the trial and reported as an AE or SAE only if the frequency, severity, or character of the condition worsens during the study. When reporting such events, it is

important to convey the concept that the preexisting condition has changed by including applicable descriptors (e.g., "more frequent headaches").

# d. Hospitalizations for Medical or Surgical Procedures

Any AE that results in hospitalization or prolonged hospitalization should be documented and reported as an SAE. If a subject is hospitalized to undergo a medical or surgical procedure as a result of an AE, the event responsible for the procedure, not the procedure itself, should be reported as the SAE. For example, if a subject is hospitalized to undergo coronary bypass surgery, record the heart condition that necessitated the bypass as the SAE.

Hospitalizations for the following reasons do not require reporting:

Hospitalization or prolonged hospitalization for diagnostic or elective surgical procedures for preexisting conditions

Hospitalization or prolonged hospitalization required to allow efficacy measurement for the study or

Hospitalization or prolonged hospitalization for scheduled therapy of the target disease of the study

# e. Assessment of Severity of Adverse Events

The adverse event severity grading scale for the NCI CTCAE (v 5 .0) will be used for assessing adverse event severity. Below Table should be used for assessing severity for adverse events that are not specifically listed in the NCI CTCAE.

# Adverse Event Severity Grading Scale for Events Not Specifically Listed in NCI CTCAE

Grade	Severity			
1	Mild; asymptomatic or mild symptoms; clinical or diagnostic observations only; or intervention not indicated			
2	Moderate; minimal, local, or non-invasive intervention indicated; or limiting age-appropriate instrumental activities of daily living a			
3	Severe or medically significant, but not immediately life-threatening; hospitalization or prolongation of hospitalization indicated; disabling; or limiting self-care activities of daily living b,c			
4	Life-threatening consequences or urgent intervention indicated d			
5	Death related to adverse event d			

NCI CTCAE = National Cancer Institute Common Terminology Criteria for Adverse Events.

 $Note: Based on the most recent version of NCI CTCAE 5, which can be found at: \\ http://ctep.cancer.gov/protocolDevelopment/electronic_applications/ctc.htm$ 

- a. Instrumental activities of daily living refer to preparing meals, shopping for groceries or clothes, using the telephone, managing money, etc.
- b. Examples of self-care activities of daily living include bathing, dressing and undressing, feeding oneself, using the toilet, and taking medications, as performed by patients who are not bedridden.
- c. If an event is assessed as a "significant medical event," it must be reported as a serious adverse event
- d. Grade 4 and 5 events must be reported as serious adverse events

# f. Pregnancy

Memorial Sloan Kettering Cancer Center IRB Number: 12-200 A(17)

Approval date: 15-Jun-2022

If a female subject becomes pregnant while receiving the Vemurafenib or within 6 months after the last dose of Vemurafenib, or if the female partner of a male study subject becomes pregnant while the study subject is receiving Vemurafenib or within 6 months after the last dose, a report should be completed and expeditiously submitted to Genentech, Inc. Follow-up to obtain the outcome of the pregnancy should also occur. Abortion, whether accidental, therapeutic, or spontaneous, should always be classified as serious, and expeditiously reported as an SAE. Similarly, any congenital anomaly/birth defect in a child born to a female subject exposed to the study drug should be reported as an SAE.

# g. AEs of Special Interest (AESIs)

AESIs are a subset of Events to Monitor (EtMs) of scientific and medical concern specific to the product, for which ongoing monitoring and rapid communication by the Investigator to the Sponsor is required. Such an event might require further investigation in order to characterize and understand it. Depending on the nature of the event, rapid communication by the trial Sponsor to other parties (e.g., Regulatory Authorities) may also be warranted.

Adverse events of special interest for this study include the following:

- Cases of potential drug-induced liver injury that include an elevated ALT or AST in combination with either an elevated bilirubin or clinical jaundice, as defined by Hy's law: Treatment-emergent ALT or AST > 3 × ULN in combination with total bilirubin > 2 × LILN
  - Treatment-emergent ALT or AST > 3 × ULN in combination with clinical jaundice
- Data related to a suspected transmission of an infectious agent by the study drug (STIAMP), as defined below:
  - Any organism, virus, or infectious particle (e.g., prion protein transmitting transmissible spongiform encephalopathy), pathogenic or non-pathogenic, is considered an infectious agent. A transmission of an infectious agent may be suspected from clinical symptoms or laboratory findings that indicate an infection in a patient exposed to a medicinal product. This term applies only when a contamination of the study drug is suspected
- Acute Kidney Injury
- Bone Marrow Toxicity
- Cutaneous Squamous Cell Carcinomas
- Gastrointestinal Polyps
- Hypersensitivity and Severe Cutaneous Reactions
- Liver Injury
- New/Second Primary Melanomas
- Non cutaneous Squamous Cell Carcinomas
- Pancreatitis
- Photosensitivity
- Potentiation of Radiation Toxicity
- Progression of RAS Mutant Malignancies
- QT Prolongation
- Retinal Vein Occlusion
- Uveitis
- VII Nerve Paralysis

# h. Other Special Situations Reports

The following other Special Situations Reports should be collected even in the absence of an Adverse Event and transmitted to Genentech:

Adverse	e Event and transmitted to Genentech:
	Data related to the Product usage during breastfeeding
	Data related to overdose, abuse, misuse or medication error (including potentially
expose	d or intercepted medication errors)
	In addition, reasonable attempts should be made to obtain and submit the age or age
group o	f the patient, in order to be able to identify potential safety signals specific to a particular
populati	on

# i. Product complaints

A Product Complaint is defined as any written or oral information received from a complainant that alleges deficiencies related to identity, quality, safety, strength, purity, reliability, durability, effectiveness, or performance of a product after it has been released and distributed to the commercial market or clinical trial.

# f. Post-Study Adverse Events

The investigator should expeditiously report any SAE occurring after a subject has completed or discontinued study participation if attributed to prior vemurafenib exposure. If the investigator should become aware of the development of cancer or a congenital anomaly in a subsequently conceived offspring of a female subject who participated in the study, this should be reported as an SAE.

# 11.3 Photosensitivity

Photosensitivity has been reported in approximately 50% of vemurafenib-treated patients in the phase 2 study of metastatic melanoma patients. The majority of cases were mild or moderate in severity. All patients should therefore be advised to avoid sun exposure and/or use sun block and lip balm (minimum of SPF 30, re-applied every 2 to 3 hours) during vemurafenib treatment and for at least 5 to 10 days after study drug discontinuation.

# 11.4 Ophthalmologic Reactions

In the phase 3 study of 675 metastatic melanoma patients, five cases of uveitis have been reported in patients treated with vemurafenib. Treatment with steroid and mydriatic ophthalmic drops may be required to manage uveitis. Patients should be routinely monitored for signs and symptoms of uveitis. Additionally, there were five patients with blurry vision, five patients with iritis and six patients with photophobia. There was one case of retinal vein occlusion in the phase 2 study of 132 metastatic melanoma patients.

# 11.5 Hypersensitivity Reactions

Serious hypersensitivity reactions, including anaphylaxis, have been reported in association with vemurafenib and upon re-initiation of treatment. Severe hypersensitivity reactions included generalized rash and erythema or hypotension. In patients who experience a severe hypersensitivity reaction, vemurafenib treatment should be permanently discontinued.

# 11.6 Dermatologic Reactions

Severe dermatologic reactions have been reported in patients receiving vemurafenib, including one case of Stevens-Johnson syndrome and one case of toxic epidermal necrolysis in the phase 3 study. In patients who experience a severe dermatologic reaction, vemurafenib

treatment should be permanently discontinued.

# 11.7 Liver Laboratory Abnormalities

Liver laboratory abnormalities have occurred with vemurafenib. Liver enzymes (transaminases and alkaline phosphatase) and bilirubin should be monitored before initiation of treatment and monthly during treatment, or as clinically indicated. Laboratory abnormalities should be managed with dose reduction, treatment interruption, or treatment discontinuation (see Section 9.2 for dose modification instructions).

# 11.8 Cutaneous Squamous Cell Carcinoma

Cutaneous squamous cell carcinoma (cuSCC) is defined as an AE of special interest. Investigator and patient should perform routine skin examination at least once per cycle (28 days). Suspicious lesions or rashes should be referred to a dermatologist. A dermatologist should perform a full skin exam during screening/baseline, after 4 weeks of treatment, and every 12 weeks thereafter until discontinuation of the drug. Patients who withdrew from the study for any reason will be followed for SCC evaluation for 6 months after study drug discontinuation, start of new antineoplastic therapy, or until death, withdrawal of consent, or lost to follow up, whichever occurs first. Additionally, at baseline, the dermatologist will perform a complete dermatological history of prior medications, non-melanoma skin cancers, including SCC and actinic keratosis and their associated treatments, and risk factors for development of cutaneous malignancies (e.g. radiation therapy, sun exposure, phototherapy, use of tanning beds, genetic conditions, and immunosuppression).

Any lesion at baseline or during treatment that is clinically suspected of representing a cuSCC, basal cell carcinoma, actinic keratosis, primary melanoma, or other skin condition identified by the dermatologist should be completely resected by a dermatologist and submitted for pathologic review. A dose reduction is not indicated for this adverse event.

# 11.9 Non-Cutaneous Squamous Cell Carcinoma

- Head and neck examination: A thorough head and neck examination to monitor for noncutaneous SCC, consisting of at least visual inspection of the oral mucosa and lymph node palpation, will be performed by the treating physician during screening/baseline, after 4 weeks of treatment, and every 12 weeks thereafter until a maximum of 6 months after discontinuation of study drug or at the start of new antineoplastic therapy, death, withdrawal of consent, or lost to follow up whichever occurs first.
- Chest CT scans: A chest CT scan will be performed during screening/baseline (up to 28 days prior to start of treatment) and, if considered clinically indicated at the discretion of treating physicians, at Cycle 3 Day 28.

# 11.10 Cardiac Toxicity

Data from the phase II trial indicate that some patients treated with vemurafenib 960mg twice a day developed mild QTc prolongation. The largest mean QTc change from baseline was 15.1 milliseconds (msec). One patient on study had a QTc change of >60 msec. Two patients (1.5%) developed QTc prolongation >500 msec. No ventricular arrhythmias have been reported to date.

The following recommendations have been developed to minimize the risk of arrhythmias on study:

- Avoid combination with other agents with known potential to lead to QTc prolongation.
- ECG should be monitored on day 1 prior to the first dose of vemurafenib, pre-dose on day 15 after study drug initiation, every 4 weeks for the next 3 cycles, and every 12 weeks thereafter.
- o If QTc interval exceeds 500 msec or the change from baseline is >60 msec, on three separate ECGs, vemurafenib treatment should be temporarily interrupted. The investigator should check electrolytes (K, Mg, and Ca), correct any electrolyte abnormalities prior of reinstitution of therapy, recheck concomitant medications to insure that non has been implicated in QTc prolongation, and rule out or control other cardiac risk factors (i.e. ischemia). Monitor ECG weekly until QTc decreases to < 500 msec and reinitiate treatment at once reduced level from 960 mg b.i.d. to 480 mg b.i.d.

- Vemurafenib should be permanently discontinued if a QTc increase meets both criteria of > 500 msec and > 60 msec change from pre-treatment values or if QTc > 500 msec or change from baseline > 60 msec is observed on two separate occasions.

# 11.11 Renal and Urinary Toxicity

A review of the Roche safety database (with an estimated exposure to vemurafenib of 28,809 patients) in May 2015 concluded that acute kidney injury is an adverse drug reaction (ADR) in patients treated with vemurafenib. This was based on 145 AKI cases with some evidence of vemurafenib causality, of which 102 cases were assessed to have strong evidence. The cases ranged within a broad spectrum, majority were mild (> 1-1.5 x ULN) to moderate (> 1.5-3 x ULN) creatinine elevations, that appear to be reversible in nature. There were 3 cases of biopsy-proven interstitial nephritis, 4 cases of biopsy-proven tubular injury/acute tubular necrosis (ATN), and 20 cases presented with DRESS or DRESS-like symptoms.

# 11.12 Reproductive Risk

The teratogenic potential of vemurafenib has not been investigated. However, women who are pregnant or nursing will be excluded from this study. Women of childbearing potential, including those who have had a tubal ligation, are required to have a negative serum pregnancy test within 7 days prior to start of treatment. Women of childbearing potential are required to use two effective methods of contraception (including one barrier method) during the study and for 6 months after discontinuation of vemurafenib. Male patients (including those who have undergone vasectomy) with female partners of childbearing potential should use a latex condom during any sexual contact and should advise their partners to use an additional method of contraception during the study and for at least 6 months after discontinuation of vemurafenib.

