#### 6.0 CRITERIA FOR SUBJECT ELIGIBILITY

# 6.1 Subject Inclusion Criteria

- 1. ≥ 18 years of age
- 2. Histologically confirmed classical HCL with one of the following:
  - Intolerance to purine analogs or considered to be poor candidates for purine analogbased therapy
  - Failure to achieve any response (CR or PR) to the initial purine analog-based therapy
  - Relapse ≤ 2 years of purine analog-based therapy
  - ≥ 2 relapses

Histologic confirmation of diagnosis will be performed at MSKCC or a participating site.

- 3. Patients who meet the standard treatment initiation criteria, as defined by ANC ≤1.0, Hgb ≤ 10.0 or PLT ≤100K
- 4. ECOG performance status of 0-2
- 5. Acceptable pre-study organ function during screening as defined as: Total bilirubin ≤ 1.5 times the upper limit of normal (ULN), aspartate aminotransferase (AST) and alanine aminotransferase (ALT) ≤ 2.5x ULN, and serum creatinine ≤ 1.5x ULN
- 6. Electrocardiogram (ECG) without evidence of clinically significant ventricular arrhythmias or ischemia as determined by the investigator and a rate-corrected QT interval (QTc, Bazett's formula) of < 480 msec.

- 7. For women of childbearing potential, agreement to the use of two acceptable methods of contraception, including one barrier method, during the study and for 6 months after discontinuation of vemurafenib
- 8. For men with female partners of childbearing potential, agreement to use a latex condom and to advise their female partner to use an additional method of contraception during the study and for 6 months after discontinuation of vemurafenib
- 9. Negative serum pregnancy test within 7 days of commencement of treatment in premenopausal women.
- 10. Agreement not to donate blood or blood products during the study and for at least 6 months after discontinuation of vemurafenib; for male partners, agreement not to donate sperm during the study and for at least 6 months after discontinuation of vemurafenib
- 11. Ability to understand and willingness to sign a written informed consent document. Willingness and ability to comply with scheduled visits, treatment plans, laboratory tests, and other study procedures.

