# Within 7 Days of Study Start:

Serum pregnancy test for women of child-bearing potential

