# 9.0 TREATMENT/INTERVENTION PLAN

#### 9.1 Administration of Vemurafenib

Patients will receive vemurafenib at a dose of 960mg orally b.i.d. continuously in cycles of 4 weeks (28 days) as outpatient. A bone marrow aspirate and/or biopsy will be performed after the first cycle for research purposes only. After the completion of the third cycle, a repeat bone marrow aspirate and/or biopsy will be performed for assessment of response and evaluation of MRD. Following the third cycle assessments, patients who achieve complete response (CR) with detectable MRD or partial response (PR) may continue with vemurafenib for up to 3 additional cycles at the treating physician's discretion (Cycles 4-6). Patients who achieve CR without MRD will be observed as part of post-treatment followup, and may be re-treated with vemurafenib after relapse (as per below). Patients who achieve no response (NR) after the initial 3 cycles of vemurafenib will be removed from the study.

After patients discontinue vemurafenib, they will be followed every 3 months as part of post-treatment followup for a total of 12 months. Patients who previously experienced CR, PR (either hematologic or MRD) or clinical benefit, but who subsequently relapse after ending treatment may be retreated with Vemurafenib until disease progression or at the treating physician's discretion. Patients who are re-treated will follow the treatment/evaluation plan as outlined in Table 3 (see Section 10). A bone marrow aspirate and/or biopsy may be performed for assessment of response at the end of the third re-treatment cycle or during a subsequent re-treatment cycle when clinically indicated.

Patients who achieve no response after the initial 3 cycles of vemurafenib will be removed from the study. In case of certain defined toxicities, dose reductions by 50% (480mg b.i.d.) or interruptions of up to 15 days are permitted. If additional dose reductions are required, vemurafenib may be reduced to 240mg oral b.i.d.

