**Management of Grade 1-4 Non-Hematologic Toxicities:** For any grade 1 and tolerable grade 2-3 toxicities, patients may continue full dose. For any intolerable grade 2-3 toxicities, dosing will be interrupted until resolution to grade 1 or less and dose reductions to 480mg b.i.d. are required, except for arthralgia in which case prednisone 5-10mg daily can be attempted first before the study drug dose reduction. If additional dose reduction is required, investigators can further reduce the dose to 240mg b.i.d. On the third appearance of any grade 2 or grade 3 adverse events despite two dose reductions, it is recommended that patients discontinue vemurafenib. For any grade 4 toxicities, patients should discontinue study treatment or, based on investigator judgment, interrupt until resolution to grade 1 or less with dose reduction to 240mg b.i.d. upon restarting study drug. Dose escalation after dose reduction is generally not recommended unless under special circumstances (i.e. increased likelihood of clinical benefit for the dose increase and no safety concern). It is recommended that patients permanently discontinue vemurafenib for a second occurrence of any grade 4 toxicities.

**Prolonged Drug Interruptions:** If a patient's study dose has been interrupted for >15 days, the patient will be considered to have discontinued from the study. If the patient is still benefiting from treatment and an interruption greater than 15 days deemed necessary by the investigator, the length of the requested interruption should be discussed with the principal investigator of the study ([name]). Restarting vemurafenib treatment after discontinuation of drug is permitted during the re-treatment phase if the investigator deems there is a clinical benefit for re-starting drug and there are no safety concerns.

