**Table 1: Evaluation on Study** 

Phase	Screening	Study Visits											
Cycle		1		2		3	4 5			6			
Day 	-28 to -1	Day 1	Day 8	Day 15	Day 22	Day 1	Day 15	Day 1	Day 28+/-4	Day 1 	Day 1	Day 1	Day 28+/-4
Informed Consent	X												
History and Physical Exam	X	X				X		X		X	X	X	
Head and Neck Exam 	X	X				X					X		
ECG	X	X		X12		X		X		X			
Serum Pregnancy Test 	X												
Dermatology Exam 	X					X					X		
CBC w/ diff, Platelets	X	X	X12	X12	X12	X	X 	X	X	X	X	X	X
Smear Review	X	X	X12	X12	X12	X		X		X	X	X	
COMP, LDH	X	X				X		X	X	X	X	X	X
Phosphorus, Uric Acid	X	X	X 	X 	X 								
PT/PTT	X												
HIV, Hepatitis B and C	X												
Adverse Events		X				X		X		X	X	X	
Review of Concomitant Medications	X	X				X		X		X	X	X	
CT Chest	X								X 				
CT Abdomen	$X^6$								X 				
Bone Marrow Aspirate and/or Biopsy	X								X				$X^8$
Research Tests													
Bone Marrow Aspirate and/or Biopsy	X 					X 			X 				X 
Peripheral Blood 	X	X 	X 	X 	X 	X		X	X	10.0			X8

<sup>1A +/- 4 day window will be allowed for completion of scheduled clinic visits (i.e. holidays, travel delays, site closures, other reasons, etc.) A +/- 7day window is allowed for Cycle 4 Day 1 to allow the adequate time for bone marrow response evaluation from Cycle 3 Day 28.

<sup>2Head and neck examination can be performed as part of general physical exam, and consist of visual inspection of the oral mucosa and lymph node palpation.21

<sup>3In women of child-bearing potential, serum pregnancy test should be obtained within 7 days prior to start of treatment.

<sup>4A window of +/- 21 days of scheduled visit (with exception of screening) is allowed for completion of these assessments.

<sup>5CT chest at Cycle 3, Day 28 will be performed if considered clinically indicated at the discretion of treating physicians (e.g. monitoring infection or pulmonary nodules).

<sup>6CT abdomen at screening will be performed if patient has intact spleen.

<sup>7CT abdomen at Cycle 3, Day 28 will be performed if splenomegaly present on screening CT abdomen.

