<sup>8Only for those who continue vemurafenib for > 3 cycles.

<sup>93-5ml of bone marrow aspirate will be collected in an EDTA-containing syringe.

<sup>103 green or purple top tubes (10cc tubes) will be collected for all patients at the specified time-points.

<sup>11For MSKCC patients only, 3 green/purple top tubes will be collected at 2-4 hours and 24 hours after the first dose of vemurafenib. For patients treated at other centers, only the pre-treatment blood samples will be drawn (3 green top tubes).

<sup>12 This test may be done locally

Cycle 3 Day 28 visit may serve as Cycle 4 Day 1 visit for patients who will continue beyond 3 cycles for high suspicion of residual disease before waiting for BMB result at the treating phsyicain's discretion.

Table 2: Procedures for End of Treatment and Post Treatment Follow Up Visits

Phase	End of Treatment	Post Treatment Follow-Up 
Time Frame	4 weeks from last treatment dose	Every 3 months post last dose
History and Physical Exam	X	X
Head and Neck Examination		X
Dermatology Evaluation 	X	X
CBC w/ diff & Platelets, COMP, LDH	X	X
Survival assessments 	X	X

<sup>1These evaluations will continue up to 12 months after study drug discontinuation.

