**Table 3: Re-Treatment Evaluation on Study** 

Phase	Study Visits									
Cycle			1			2		3	"X"	
$\mathrm{Day}^1$	Day 1	Day 8	Day 15	Day 22	Day 1	Day 15	Day 1	Day 28+/-4	Day 1	As clinically indicated
History and Physical Exam	X				X		X		X	
Head and Neck Exam 	X				X					
ECG	X		X8		X		X		$X^{10}$	
Dermatology Exam 							X			X
CBC w/ diff, Platelets	X	X8	X8	X8	X	X8	X	X	X	
Smear Review	X	X8	X8	X8	X		X		X	
COMP, LDH	X				X		X	X	X	
Phosphorus, Uric Acid	X	X8	X8	X8						
PT/PTT										
HIV, Hepatitis B and C Testing										
Adverse Events	X				X		X		X	
Review of Concomitant Medications	X				X		X		X	
CT Chest								X 		
CT Abdomen								X 		
Bone Marrow Aspirate and/or Biopsy								X 		X 
Research Tests		ı	1	ı			1	•		•
Bone Marrow Aspirate and/or Biopsy 								X 		X 
Peripheral Blood 	X				X		X	X 		X 

<sup>1A +/- 4 day window will be allowed for completion of scheduled clinic visits (i.e. holidays, travel delays, site closures, other reasons, etc.)

<sup>2A +/- 14 day window is allowed for this assessment.

<sup>3This evaluation may be perforned locally

<sup>4Survival assessment will be collected on an ongoing basis and at least every 3 months.

<sup>5If clinically indicated

<sup>2Head and neck examination can be performed as part of general physical exam, and consist of visual inspection of the oral mucosa and lymph node palpation.

<sup>3A window of +/- 21 days of scheduled visit is allowed for completion of these assessments.

<sup>4CT chest at Cycle 3, Day 28 will be performed if considered clinically indicated at the discretion of treating physicians (e.g. monitoring infection or pulmonary nodules).

<sup>5CT abdomen at Cycle 3, Day 28 will be performed if splenomegaly present on screening CT abdomen.

<sup>63-5ml of bone marrow aspirate will be collected in an EDTA-containing syringe.

<sup>73 green or purple top tubes (10cc tubes) will be collected for all patients at the specified time-points.

<sup>8This test may be done locally

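### The re-treatment schedule (Table 3) has no pregnancy test before vemurafenib is restarted, although a negative serum test within 7 days is required before the first start

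*Combined protocol and SAP*

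**What the plan says.** Four places require a pregnancy test before treatment:

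- Section 6.1, item 9: "Negative serum pregnancy test within 7 days of commencement of treatment in premenopausal women".
- Section 8.0, in the list for the 7 days before study start: "Serum pregnancy test for women of child-bearing potential".
- Table 1, footnote 3: "In women of child-bearing potential, serum pregnancy test should be obtained within 7 days prior to start of treatment". The table row has a single mark, at screening.
- Section 11.12: women of childbearing potential, expressly including those with a tubal ligation, "are required to have a negative serum pregnancy test within 7 days prior to start of treatment". The same paragraph says that teratogenicity has not been studied, and it requires two contraceptive methods while on study and for 6 months after the drug is stopped.

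Re-treatment after relapse is allowed in Sections 1.0, 4.2 and 9.1. Section 9.1 says: "Patients who are re-treated will follow the treatment/evaluation plan as outlined in Table 3". Section 9.2 adds that restarting after discontinuation is "permitted during the re-treatment phase if the investigator deems there is a clinical benefit for re-starting drug and there are no safety concerns". For the time off drug, Table 2 sets a visit 4 weeks after the last dose and then one every 3 months; its footnote 1 reads "These evaluations will continue up to 12 months after study drug discontinuation".

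**The concern.** Re-treatment is a second start of the same drug after a period without it. At the first start the protocol does not rely on contraception alone; it also demands a recent negative test, even after tubal ligation. At the second start, the schedule that governs the visit leaves the test out, and no text explains why.

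What is at stake is fetal exposure to a drug whose teratogenicity is unknown. Pregnancy is an exclusion at entry (Section 6.2, item 1), but Section 13.0 ties removal for ineligibility to the pretreatment evaluation and does not list pregnancy separately. Nothing in the schedule would therefore detect an early pregnancy before the restart.

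**Working it through.** The plan gives no figure to reproduce, so the check sets the three schedules side by side and then illustrates the time since the last scheduled test.

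**Scheduled serum pregnancy tests**

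| Schedule | Period | Tests |
|---|---|---|
| Table 1 | Screening and Cycles 1–6 | 1 (screening) |
| Table 2 | Off drug: 4 weeks, then months 3, 6, 9 and 12 (1 + 4 = 5 visits) | 0 |
| Table 3 ("Table 3: Re-Treatment Evaluation on Study") | Re-treatment | 0 |

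On re-treatment Cycle 1 Day 1, Table 3 marks history and physical, head and neck exam, ECG, blood count, smear, chemistry with LDH, phosphorus and uric acid. It has no column before Day 1, and none of its footnotes mentions pregnancy. Loss of a row in text extraction is unlikely: Table 3 still prints the PT/PTT and HIV/hepatitis rows with no marks in them, whereas the pregnancy row is absent altogether.

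**Time from first dose to restart (illustration)**

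The documents give no minimum or maximum interval to re-treatment. Two scenarios are assumed, with 28-day cycles, 3 months taken as 91 days and 12 months as 365 days:

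- Short: 3 cycles, restart at the 3-month visit. 3 × 28 + 91 = 84 + 91 = 175 days.
- Long: 6 cycles, restart at the 12-month visit. 6 × 28 + 365 = 168 + 365 = 533 days.

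The entry test may be up to 7 days before the first dose, so the last scheduled test is at most 175 + 7 = 182 days old in the short scenario and 533 + 7 = 540 days old in the long one.

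**Contraception over the same interval**

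The requirement runs through the study and for 6 months after discontinuation. If the study is taken to include post-treatment follow-up, contraception covers the whole of Table 2. If a patient counts 6 months from her last dose, a restart at month 12 comes 12 − 6 = 6 months after the requirement ended. The text does not settle which reading applies.

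**The case against.** The strongest reply is that no rule is broken. The protocol's scheme can be read as one test at entry followed by continuous contraception. Table 1 schedules no repeat test over as many as six cycles, and Table 3 also leaves the other screening-only laboratory tests unmarked, which fits a decision not to repeat entry screening. Alternatively, the start of treatment in Section 11.12 might be read to include a restart, in which case only the schedule entry is missing. In addition, two contraceptive methods are required, there is a history and examination on Day 1, restarting is conditional on there being no safety concerns, and an investigator is free to order the test.

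The number affected is also uncertain. Accrual had closed by 17 August 2016. A patient starting about then would finish six cycles around February 2017 and 12 months of follow-up around February 2018, allowing for some delay from interruptions. The documents do not show that any woman of childbearing potential was still to be re-treated when this version was approved in June 2022.

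Much of this stands. The point is an omission and not a contradiction, and it may affect nobody. But continuous dosing under contraception differs from restarting after a gap in which contraception may have lapsed. None of the safeguards requires a test, and the doubt about what counts as a start is itself a reason to clarify the text. The dates cut both ways: with accrual closed, any new start of drug under the current text is, by inference, a re-treatment start under Table 3.

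**Conclusion.** The concern holds. The schedule for re-treated patients omits a safety test that the protocol requires in four places for the first start, and no other schedule supplies it. The scheduled counts are 1, 0 and 0 across Tables 1 to 3. In the illustrations the last scheduled test would be up to 182 or 540 days old at restart; these figures depend on the assumed restart times, because the plan states none.

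The conclusion assumes that Section 11.12 refers to study entry, which is its most natural reading. On the wider reading the requirement exists, but Table 3 does not put it into effect. The number of re-treated women of childbearing potential is not given and may be few or none of the 36 planned patients. The two-stage design and the response-rate analysis are unaffected. The change should be made because the possible harm is irreversible and the remedy is cheap.

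**What to change.** Add to Table 3 a row or footnote for women of childbearing potential: *negative serum pregnancy test in the 7 days preceding re-treatment Cycle 1 Day 1*. Add a clause to Section 11.12 stating that the test applies to every start of vemurafenib, re-treatment included.

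The cost is one table entry, one clause and one extra blood test per re-treatment start in a few women at most. Sample size, endpoint and analysis do not change.
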